Thyroid hormones, thyroxine (T4) and triiodothyronine (T3), are produced in the follicular cells of the thyroid gland and can impact nearly every cell in the human body. They are essential to the human metabolism, influence the basal metabolic rate, bone growth, neural maturation, the body's sensitivity to catecholamines, cell development and differentiation as well as protein, fat and carbohydrate metabolism. With about 5000 µg, the thyroid is the largest storage of T4.^{1(p303)} Therefore, the maintenance of adequate thyroid hormones levels is crucial for the patient's quality of life after a hemithyroidectomy. The thyroid is constituted of a right and a left lobe as well as a connecting isthmus. In most patients, the right lobe is significantly larger than left lobe.² In a 2009 study by Ying and Yung, the right lobe was 6.8ml as opposed to the left lobe with a volume of 5.66ml.³ Although the remaining lobe adapts and continues to grow up to 30% from its original size to compensate for the loss,⁴, thyroid hormone supplementation is required in approximately 22% of all patients after thyroid lobectomy.^{5,6} In order to predict the necessity of thyroid hormone replacement therapy after hemithyroidectomy, risk factors such as a higher TSH before surgery, but also the resected thyroid volume have been identified in the past. Surprisingly, the resected thyroid volume showed significant negative correlation with postoperative TSH levels in a 2015 study by Lee et al.⁵ Previous studies aiming at optimizing post-surgery levothyroxine dosages incorporated sex, age, body surface area (BSA) and body mass index (BMI) but not if the right of left thyroid gland was resected into their calculations.^{7,8} Therefore, the study at hand aims at investigating a possible difference in levothyroxine requirements depending on the side of the resection to ensure adequate treatment.

2 Research questions and aims

- **Research Questions:** We hypothesize a possible influence of right vs left hemithyroidectomy on developing postoperative hypothyroidism as well as treatment dosage.
- **The aim** of this study is to be able to better predict the necessity, dosage and starting point of levothyroxine treatment after a hemithyroidectomy.

3 Study design

The study at hand is an exploratory retrospective study conducted on approximately 1250 patients who received a hemithyroidectomy at the Medical University of Vienna, Department of General Surgery, Division of Endocrine Surgery. A possible confounding factor is that the underlying conditions such as goiter or nodules which lead to the surgery might differ in the patients.

4 Patients

All patients who received a hemithyroidectomy at the Department of General Surgery, Division of Endocrine Surgery between 1994 and 2018 will be included in the study which are around 50 per year totalling around 1250 patients. Due to the study design, no power calculations have been conducted beforehand. However, considering similar studies^{5,6}, this sample size was deemed sufficient in order to achieve valid results and a statistical power of 0.8.

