4.2 Exclusion criteria

- Radiation therapy
- Pregnancy
- Previous thyroid surgery (e.g. nodule removal surgery)

Differences in Levothyroxine requirements after hemithyroidectomy

5 Primary and secondary parameters

The occurrence of post-surgery hypothyroidism and levothyroxine dosage is the primary outcome parameter. The secondary outcome parameter is the timespan between hemithyroidectomy and the need for levothyroxine treatment.

6 Methodology

The list of patients who underwent a hemithyroidectomy will be provided by the IT4Science department via a data extraction from the RDA database. Further information necessary for the analysis (side of hemithyroidectomy, type and dosage of treatment) will be extracted from the AKH-Informationsmanagement (AKIM) at the General Hospital of Vienna (AKH), analyzed and pseudonymized by [name] and, then, safely secured on a server at the Chiari Stoffwechsellambulanz.

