6.1 Statistical analysis

The collected data will be analyzed by descriptive statistics and illustrated in SPSS (Version 22) by using graphs, tables and boxplots. All data is password protected and anonymized to ensure adequate privacy protection.

Normally distributed data will be described by calculating median, mean and standard deviation. Patient baseline characteristics will be described as percentages and frequencies for categorical variables or mean and median values and standard deviation for normally distributed continual variables. In order to ensure comparability, a Levene's Test for Equal Variances will be performed. Differences of characteristics between the groups will be analyzed by unpaired T- tests for continuous variables. Possible confounding factors such as age, sex, underlying disease and BMI will be identified and adjusted for in a multiple logistic regression model.

In order to compare the levothyroxine dosages, a parametrical test (t-test) with a significance level of $p < 0.05$ will be performed. Adequate transformations such as the Levene's Test for Equal Variances will be applied to deal with not normally distributed residues and, thus, ensure comparable variances. For illustrational purposes, bar charts, histograms and boxplots will be used.

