6.1.1 Null hypothesis

H₀: The side of the resected thyroid lobe in a hemithyroidectomy does not influence the hypothyroidism occurrence and levothyroxine dosage requirements after surgery.

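### The plan states both an associational and a predictive aim, but its hypotheses and analyses serve only the first, so it cannot support a claim of better prediction

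*Combined protocol and SAP*

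**What the plan says.** There are two statements of purpose. The last sentence of the background says the study will investigate whether levothyroxine requirements differ by side of resection. The research question in section 2 agrees: "We hypothesize a possible influence of right vs left hemithyroidectomy on developing postoperative hypothyroidism as well as treatment dosage". The next bullet gives the aim as "to be able to better predict the necessity, dosage and starting point of levothyroxine treatment after a hemithyroidectomy".

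The null hypothesis in 6.1.1 is "The side of the resected thyroid lobe in a hemithyroidectomy does not influence the hypothyroidism occurrence and levothyroxine dosage requirements after surgery". The one in 6.1.2 asks whether the side comparison differs between men and women. Neither mentions predictive performance.

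Section 6.1 plans descriptive statistics and three inferential steps:
- Patient characteristics are compared by unpaired t-tests where they are continuous.
- The only regression model named is introduced as a means of adjustment: "Possible confounding factors such as age, sex, underlying disease and BMI will be identified and adjusted for in a multiple logistic regression model".
- Dose is handled by a separate two-group comparison, for which the text reads "In order to compare the levothyroxine dosages, a parametrical test (t-test) with a significance level of" and then gives a 5% threshold.

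Section 5 adds that "The secondary outcome parameter is the timespan between hemithyroidectomy and the need for levothyroxine treatment". Section 6.1 names no method for this outcome.

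On existing predictors, the background says that "risk factors such as a higher TSH before surgery, but also the resected thyroid volume have been identified in the past". It adds that earlier dosing work used sex, age, BSA and BMI, but not side.

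**The concern.** To predict better, one must predict better than something. The background supplies the comparator: preoperative TSH, resected volume and the patient characteristics used in earlier dosing work. Showing that side improves on these needs a measure of how well need, dose or start is predicted, taken with and without side. The plan contains no such measure for any of the three.

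A t-test or an adjusted odds ratio answers another question, namely whether the groups differ on average. With about 1250 patients, that answer can be a clear yes while side says very little about the individual patient. A reader who holds the results against the aim in section 2 would then have an association but no evidence on prediction.

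**Working it through.** **1. Aim against analysis**

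| Part of the predictive aim | Planned in 6.1 | What it yields |
|---|---|---|
| Necessity | Logistic regression adjusting for confounders | Adjusted association of side with hypothyroidism |
| Dosage | t-test | Difference in mean dose by side |
| Starting point | No method named | Nothing specified |

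No section plans discrimination, calibration, validation, or a comparison of models with and without side. The covariates in 6.1 are age, sex, underlying disease and BMI, given as examples. Preoperative TSH and resected volume are not among them, nor among the variables section 6 names for extraction. Both lists may be incomplete, so their use is not ruled out; it is just not planned.

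**2. The plan's own figures**

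Section 4: 1994 to 2018 inclusive is 25 years; 25 × 50 = 1250. The sample size reproduces as a head count. The stated power of 0.8 can be neither reproduced nor refuted, because no effect size or left/right split is given.

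**3. How far significance can lie from prediction**

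Inputs from the documents: N = 1250; overall rate p = 0.22 (background). Assumptions: equal split (625 per side) and a two-sided 5% test.

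- SE of the difference ≈ √(2 × 0.22 × 0.78 / 625) = 0.0234.
- Difference detectable with 80% power = (1.96 + 0.84) × 0.0234 ≈ 0.066, that is 25.3% versus 18.7% (odds ratio 1.47).
- For side as sole predictor, c = 0.5 + 0.5 × [P(higher-risk side | event) − P(higher-risk side | no event)].
- P(higher-risk side | event) = 0.2528 / (0.2528 + 0.1872) = 0.575.
- P(higher-risk side | no event) = 0.7472 / (0.7472 + 0.8128) = 0.479.
- c = 0.5 + 0.5 × (0.575 − 0.479) = 0.548.

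Other cases by the same method:

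| Case | Difference (points) | c-statistic, side alone |
|---|---|---|
| 50:50, 50% power | 4.6 | 0.533 |
| 50:50, 80% power | 6.6 | 0.548 |
| 55:45, 80% power | 6.6 | 0.547 |
| 60:40, 80% power | 6.7 | 0.546 |
| 50:50, 90% power | 7.6 | 0.555 |
| 50:50, 27% vs 17% (99% power) | 10 | 0.573 |

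In the 50:50, 80% power case the Brier score falls from 0.22 × 0.78 = 0.1716 to 0.5 × (0.2528 × 0.7472 + 0.1872 × 0.8128) = 0.1705, a relative gain of about 0.6%.

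**4. Dose**

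Assume that 22% of 1250 = 275 patients are treated, split equally (137.5 per side). The detectable standardised difference is (1.96 + 0.84) × √(2/137.5) = 0.34 SD. Side then explains d²/(d² + 4) = 0.338² / (0.338² + 4) ≈ 2.8% of dose variance.

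**The case against.** **The narrower aim is already there.** The background sentence, the research question and both null hypotheses concern association, and 6.1 matches them. This stands. It would be wrong to say that the plan cannot answer its own aim; it cannot answer one of its two aim statements.

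**Prediction may be meant loosely.** The background speaks of predicting need by identifying risk factors, and section 3 calls the study exploratory. On that reading the adjusted logistic regression is relevant, and full prediction-model development is more than such a study must do. This stands in part. It justifies modest analyses and makes rewording a fair solution. But the aim says better, and names dose and starting point too. Dose has no named multivariable model, and starting point has no named method.

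**The c-statistics describe side alone.** They do not measure what side adds to age, sex, BMI, TSH or volume, and any binary factor with an odds ratio near 1.5 and an even split would look similar. This stands. The figures show only that significance does not imply useful prediction.

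**A stronger reading is tempting:** that a significant side effect would be reported as improved prediction. A reader might infer this from the aim and from the remark in section 8 that the results can be used to optimise care. The documents contain no reporting rule and no planned conclusion of that kind, so they do not support it.

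**Conclusion.** The point holds as a mismatch between one of two stated aims and the planned analyses. The associational aim is served for need and dose. The predictive aim is not served for any of its three parts, so the plan as written cannot support a claim of better prediction.

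No planned test is shown to be wrong. The c-statistic of 0.548 (0.546 to 0.548 for splits from 60:40 to 50:50) and the 2.8% of dose variance are illustrations. They rest on the 22% rate from the background and on assumptions the documents do not state: the split, two-sided testing and, for dose, 275 treated patients. The true added value of side could be smaller or larger; the plan has no step that would show which.

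**What to change.** Choose one of two routes.

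**Narrow the aim.** In section 2, state the aim as estimating the association of resection side with hypothyroidism, levothyroxine dose and time to levothyroxine, and make no prediction claim in the conclusions.

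**Or add the comparison to 6.1:**
- *Need:* fit the planned logistic model with and without side, in the same patients, and report the optimism-corrected change in c-statistic or Brier score (for example by bootstrap). Include preoperative TSH and resected volume if the records hold them. If they do not, say that added value over these known predictors was not tested.
- *Dose:* fit a linear model with and without side and report the change in R-squared or mean absolute error.
- *Starting point:* name a time-to-event model for time to levothyroxine and make the same comparison.

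A change in calibration slope should not be used to show added value: the apparent slope of a maximum-likelihood logistic model is 1 with or without side, and its optimism correction reflects overfitting.

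The first route costs a reworded sentence and a narrower aim. The second costs a little extra analysis, mostly on data already planned; only TSH and volume depend on availability.

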4.1 Inclusion criteria

- 18 years
- Males and females
- St.p. hemithyroidectomy

4.2 Exclusion criteria

- Radiation therapy
- Pregnancy
- Previous thyroid surgery (e.g. nodule removal surgery)

Differences in Levothyroxine requirements after hemithyroidectomy

5 Primary and secondary parameters

The occurrence of post-surgery hypothyroidism and levothyroxine dosage is the primary outcome parameter. The secondary outcome parameter is the timespan between hemithyroidectomy and the need for levothyroxine treatment.

6 Methodology

The list of patients who underwent a hemithyroidectomy will be provided by the IT4Science department via a data extraction from the RDA database. Further information necessary for the analysis (side of hemithyroidectomy, type and dosage of treatment) will be extracted from the AKH-Informationsmanagement (AKIM) at the General Hospital of Vienna (AKH), analyzed and pseudonymized by [name] and, then, safely secured on a server at the Chiari Stoffwechsellambulanz.

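### Patients already hypothyroid or on levothyroxine before surgery are neither excluded nor separated, although the study asks about hypothyroidism that develops, and treatment that starts, after surgery.

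*Combined protocol and SAP*

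**What the plan says.** Section 2 (Research questions and aims) hypothesises a "possible influence of right vs left hemithyroidectomy on developing postoperative hypothyroidism", and the aim is to "better predict the necessity, dosage and starting point of levothyroxine treatment after a hemithyroidectomy". Section 5 follows on: "The occurrence of post-surgery hypothyroidism and levothyroxine dosage is the primary outcome parameter", and "The secondary outcome parameter is the timespan between hemithyroidectomy and the need for levothyroxine treatment".

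The population is set more widely. Section 4 opens with "All patients who received a hemithyroidectomy at the Department of General Surgery" in the years 1994 to 2018, about 1250 people. Section 4.1 asks only for age, either sex and a completed hemithyroidectomy. Section 4.2 lists radiation therapy, pregnancy and "Previous thyroid surgery (e.g. nodule removal surgery". None of these conditions concerns thyroid function or thyroid medication before the operation.

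Section 6 gives as examples of the data to be extracted "side of hemithyroidectomy, type and dosage of treatment". Section 6.1 adjusts for age, sex, underlying disease and BMI in a logistic model and compares doses by t-test. The background names a higher TSH before surgery as a known risk factor, but preoperative TSH is not mentioned again.

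**The concern.** A patient who is hypothyroid or on levothyroxine on the day of surgery cannot newly develop the condition. The eligibility rules still admit that patient to all three outcomes:

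- **Occurrence.** The patient can be counted as a case of post-surgery hypothyroidism, whichever lobe was removed.
- **Dose.** The recorded dose partly reflects a need that existed before the operation.
- **Time to levothyroxine need.** The interval has no meaningful value, because treatment or the need for it came before its starting point. This is so for every such patient, however few there are.

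If prior cases are equally common after right and left resections, they add the same background to both groups and pull the comparison toward no difference. If they are more common on one side, they can produce a side difference that the operation did not cause. If the handling is chosen after the data have been seen, the choice may be influenced by the result.

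**Working it through.** **Plan's own figure.** About 50 patients a year over 1994 to 2018 inclusive is 50 × 25 = 1250, which agrees with section 4. The power of 0.8 stated there cannot be reproduced, because no effect size or right-to-left ratio is given.

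**Is there a rule anywhere?** Sections 4, 4.1, 4.2, 5, 6 and 6.1 contain no exclusion, stratification or separate analysis by preoperative thyroid status. The nearest candidate is underlying disease in section 6.1. Section 3 describes underlying conditions as those that led to the operation, such as goiter or nodules. The covariate also enters only the logistic model, so it gives no rule for dose or time.

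**Illustration of size for occurrence.** Inputs:
- From the documents: total N of 1250; significance level 0.05; about 22% needing supplementation (background: "thyroid hormone supplementation is required in approximately 22% of all patients after thyroid lobectomy").
- Assumed: equal split, 625 per side; two-sided test; new-onset rates p1 = 0.253 and p2 = 0.187 (average 0.22, odds ratio 1.47), chosen because they give power of about 0.80; prevalence q of prior cases, equal on both sides.

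Formulas:
- Prior cases counted as events: rates a = q + (1 − q)p1 and b = q + (1 − q)p2, with n = 625 per side.
- Prior cases excluded: rates p1 and p2, with n = 625(1 − q) per side.
- Power = Φ[(|a − b| − 1.96·SE0)/SE1], with m = (a + b)/2, SE0 = √(2m(1 − m)/n) and SE1 = √((a(1 − a) + b(1 − b))/n).

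Worked at q = 0.05:
- Counted: a = 0.05 + 0.95 × 0.253 = 0.2904; b = 0.05 + 0.95 × 0.187 = 0.2277; difference 0.0627; SE0 = 0.02478; SE1 = 0.02472. Power = Φ[(0.0627 − 0.0486)/0.02472] = Φ(0.57) = 0.716.
- Excluded: n = 593.75; difference 0.066; SE0 = 0.02404; SE1 = 0.02397. Power = Φ[(0.066 − 0.0471)/0.02397] = Φ(0.79) = 0.785.

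| Assumed prevalence | Difference if counted | Odds ratio if counted | Power, counted | Power, excluded |
|---|---|---|---|---|
| 0% | 6.6 points | 1.47 | 0.805 | 0.805 |
| 1% | 6.5 points | 1.45 | 0.787 | 0.801 |
| 2% | 6.5 points | 1.43 | 0.769 | 0.797 |
| 5% | 6.3 points | 1.39 | 0.716 | 0.785 |

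**If the 22% already includes prior users.** The background does not say. The new-onset average is then (0.22 − q)/(1 − q), which is 20.4% at q = 0.02 and 17.9% at q = 0.05. With the odds ratio held at 1.47, power counted versus excluded is 0.743 versus 0.775, and 0.629 versus 0.719. At 5%, about half of the fall from 0.805 comes from having fewer new cases (0.805 to 0.719). Only the rest (0.719 to 0.629) comes from counting prior ones.

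**Dose comparison.** Assume that it is made among treated patients and that all prior cases are treated. Their share of the treated is q/(q + (1 − q) × 0.22): 0.02/0.2356 = 8.5% and 0.05/0.259 = 19.3%. If 22% is the total, the share is q/0.22, or 9.1% and 22.7%. The effect on the t-test cannot be computed, because the documents give no dose means or standard deviations.

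**Unequal prevalence, no true side effect.** Assume 22% new onset on both sides. With prior cases at 6% and 4%, the observed rates are 26.7% and 25.1%, and a significant result in that direction has probability about 0.09 against a nominal 0.025. With 10% and 5%, the rates are 29.8% and 25.9% and the probability is about 0.34. The documents do not suggest that such an imbalance exists.

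**The case against.** The strongest reply is that the wording already means new onset: hypothyroidism that develops, occurrence after surgery, a starting point, a timespan from the operation. A sensible analyst would not count a patient treated for years as an event. This is fair as to intent. A reader might infer that the plan defines its outcome to include prior cases, or that it contradicts itself. The documents support neither reading. What is missing is the rule that carries the intent into the population and the three analyses.

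A reader might also infer from section 6 that preoperative status will not be collected. That goes too far. The parenthesis there also omits age, sex, BMI and underlying disease, all of which section 6.1 uses, as well as the treatment start date that section 5 needs. The list is plainly incomplete, and its silence proves little. The confounder list in section 6.1 is open too, so preoperative TSH could still be added. That would be an adjustment in the occurrence model only; it would not settle who belongs in the dose comparison or define a time for someone already treated.

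Third, every power figure rests on an assumed prevalence, side effect and split. At 1% to 2% the loss against exclusion is only 1 to 3 percentage points, and nothing in the documents places this cohort at 5%. This stands: the figures show a mechanism and a range, and do not estimate the loss in this study.

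Last, the study is exploratory. It nevertheless states a null hypothesis on occurrence and dose, a 0.05 level and a hoped-for power of 0.8, so who is counted matters.

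**Conclusion.** The concern holds as a gap between the question and the analysis population. The eligibility rules admit patients who cannot newly develop the outcome, and no section says how they are handled for occurrence, dose or time. For the time outcome the problem exists as soon as one such patient is included. For occurrence and dose the size is unknown, because the documents give neither the prevalence nor its balance by side. Under the stated assumptions the loss of power for occurrence is small at 1% to 2% prevalence (0.77 versus 0.80 at 2%) and becomes material at about 5% (0.72 versus 0.78). A reader might conclude that the side comparison is biased or seriously underpowered for this reason; the documents do not show that. The change is worth making before extraction because it is cheap and because a rule set afterwards could depend on the results.

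**What to change.** 1. Add to the data extraction: levothyroxine use before surgery and, where available, preoperative TSH or a recorded diagnosis of hypothyroidism.
2. State in section 4.2 or section 5 that the primary occurrence, dose and time analyses are restricted to patients not known to be hypothyroid or treated before surgery.
3. Report pre-treated patients separately.
4. Keep patients of unknown preoperative status in the main analysis, and add a sensitivity analysis without them.

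The cost is a short protocol edit and two or three fields from hospital records that are already being used. N falls somewhat below 1250, older records may be incomplete, and the results apply only to patients not known to be hypothyroid before surgery.

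To show the cost, assume 5% prevalence and 20% unknown status. Keeping the unknowns leaves 625 × (0.80 × 0.95 + 0.20) = 600 per side. Residual prevalence is 0.20 × 0.05/0.96 = 1.0%, and power is about 0.77, against 0.72 with no rule. Without the unknowns there are 625 × 0.80 × 0.95 = 475 per side and power is about 0.69, so that analysis serves as a check and not as the main result. Stratifying by preoperative status would also be defensible; what matters is that one rule is written down for each outcome.

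### The time to levothyroxine has no specific analysis, none of the named methods can analyse it while keeping patients who have not started, and occurrence of hypothyroidism has no time window (cheap improvement)

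*Combined protocol and SAP*

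**What the plan says.** Section 5 of the combined protocol and SAP sets the outcomes: "The occurrence of post-surgery hypothyroidism and levothyroxine dosage is the primary outcome parameter", followed by "The secondary outcome parameter is the timespan between hemithyroidectomy and the need for levothyroxine treatment". Section 2 gives the aim as being able to "better predict the necessity, dosage and starting point of levothyroxine treatment after a hemithyroidectomy", so timing is part of what the study sets out to answer.

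Section 3 describes an "exploratory retrospective study conducted on approximately 1250 patients". Section 4 sets the period: "All patients who received a hemithyroidectomy at the Department of General Surgery, Division of Endocrine Surgery between 1994 and 2018 will be included". The introduction cites, with no time horizon, that "thyroid hormone supplementation is required in approximately 22% of all patients after thyroid lobectomy".

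Section 6.1 opens with "The collected data will be analyzed by descriptive statistics". It then names Levene's test, unpaired t-tests for continuous characteristics, one multiple logistic regression whose outcome is not stated, and a t-test at the 0.05 level for dosage. It mentions neither the timespan nor censoring, end of follow-up or a time-to-event method. The hypotheses in 6.1.1 and 6.1.2 cover occurrence and dosage only.

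On data, section 6 says: "Further information necessary for the analysis (side of hemithyroidectomy, type and dosage of treatment) will be extracted". No dates are named there.

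**The concern.** A timespan to an event is observed only in patients who have the event. A mean, median, boxplot or t-test needs a value for each patient, so patients who have not started drop out. Logistic regression keeps them, but as a yes/no outcome that discards the timing. Followed as written, the plan can therefore give only a time among starters. That time is cut short by the length of each patient's record, because late starters are missed when observation is brief.

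Occurrence has a related gap. With no window, minimum follow-up or cut-off, ever/never hypothyroidism means something different for a patient operated on in 1994 and one operated on in 2018. Length of follow-up is not among the covariates named for the logistic model, although that list is open-ended.

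At stake is the starting-point part of the aim, which would not be answered for all patients, and the interpretability of the occurrence percentage.

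**Working it through.** **1. The plan's own count.** Section 4 gives about 50 patients a year for 1994 to 2018: 50 × (2018 − 1994 + 1) = 50 × 25 = 1250. This reproduces the stated figure.

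**2. Patients without an observed timespan.** With the cited 22%: 0.22 × 1250 = 275 starters, and 1250 − 275 = 975 (78%) with no value.

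**3. Effect of staggered entry alone.** Assumptions, none of them from the documents: 22% ever start; onset among them is exponential with rate λ = ln 2 / median; surgery dates are uniform over 25 years; the cut-off is the end of 2018; there is no other loss. For follow-up a uniform on (L, U):

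observed occurrence = 0.22 × [1 − (e^(−λL) − e^(−λU)) / (λ(U − L))].

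Median 1 year, so λ = 0.693:
- All surgeries (0 to 25 years): 0.22 × [1 − 1/(0.693 × 25)] = 0.22 × 0.9423 = 20.7%.
- 2014-2018 (0 to 5 years): 0.22 × [1 − (1 − 1/32)/3.466] = 0.22 × 0.7205 = 15.9%.

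The starters-only mean time is E[λ((1 − e^(−λa))/λ² − a·e^(−λa)/λ)] / E[1 − e^(−λa)], averaged over a.

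| Median onset (years) | Occurrence, all | 2014-2018 | 1994-1998 | All, cut-off 2 years later | Starters-only mean (true), years |
|---|---|---|---|---|---|
| 0.5 | 21.4% | 18.8% | 22.0% | 22.0% | 0.70 (0.72) |
| 1 | 20.7% | 15.9% | 22.0% | 21.7% | 1.35 (1.44) |
| 3 | 18.2% | 9.0% | 21.9% | 19.6% | 3.44 (4.33) |

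**4. Effect of short records.** Add an exponential record length with mean m (assumed) and replace λ by k = λ + 1/m, so that occurrence = 0.22 × E[(λ/k)(1 − e^(−ka))]. Median 1 year, m = 2: k = 1.193, λ/k = 0.581, and 0.22 × 0.581 × (1 − 1/(1.193 × 25)) = 12.3%. For m = 10, 5, 2 and 1 years, occurrence is 18.3%, 16.3%, 12.3% and 8.8%. The starters-only mean is 1.19, 1.07, 0.81 and 0.58 years against a true 1.44.

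**5. Side comparison of occurrence.** Simulation with no side effect, 625 per side, 20,000 replicates, median onset 1 year and equal follow-up by side. The unadjusted log odds ratio test rejected in 5.1% (staggered entry only), 5.2% (m = 5), 5.0% (m = 2) and 4.9% (m = 1).

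**6. What the proposed method can and cannot repair.** Simulation of 2,000,000 patients, median onset 1 year. True occurrence at 2 years is 0.22 × (1 − 0.25) = 16.5%.

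| Mean record (assumed) | Kaplan-Meier | Lost counted as event-free | Records reaching 2 years only |
|---|---|---|---|
| 2 years for all | 16.5% | 11.3% | 16.6% |
| Starters 4, others 2 | 19.5% | 13.3% | 23.8% |
| Starters 2, others 4 | 14.1% | 11.3% | 10.9% |

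Kaplan-Meier is right when length of record is unrelated to starting, and biased either way when it is related. Counting lost patients as event-free is low in all three cases. Restricting to long records is not a bound in either direction.

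**The case against.** The strongest reply has four parts.

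First, the study is exploratory, the timespan is in neither hypothesis, and the general descriptive sentence covers all collected data. This stands in part. It would be wrong to infer that the outcome has no analysis at all; what is missing is a specific one. It would also be wrong to infer that the plan prescribes a t-test of times among starters, since the only t-test tied to an outcome is for dosage.

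Second, a starting point can be read as conditional on needing treatment, so that patients who never need it are not lost information. That is a legitimate descriptive quantity, but it is still cut short by follow-up, and at extraction a patient who never starts cannot be told from one who has not started yet.

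Third, the harm is small unless records are short. This stands: the large figures in step 4 rest on assumed record lengths. A reader might infer that the left/right comparison is invalid or badly underpowered. The documents do not support that, because nothing shows follow-up differing by side. In a simulation with an assumed hazard ratio of 1.4, 625 per side and equal follow-up, a plain ever/never comparison had 76% power against 77% for the log-rank test with staggered entry only. The figures were 68% against 69% with a mean record of 5 years, and 53% against 55% with 2 years.

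Fourth, the extraction list is not exhaustive. It also omits age, sex and BMI, which the analysis uses, so the missing dates do not show that they will go uncollected. This stands. The practical point is only that adding them late means returning to the records.

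**Conclusion.** The point holds as a cheap improvement. The textual gap is certain: a declared secondary outcome and part of the aim have no specific analysis, the named methods cannot analyse the timespan while keeping patients who have not started, and occurrence has no time window.

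The size is less certain. Under 22% ever starting, exponential onset, uniform surgery dates and an end-2018 cut-off, staggered entry lowers overall occurrence by 0.6, 1.3 or 3.8 percentage points for a median onset of 0.5, 1 or 3 years. The loss is concentrated in recent surgeries: 3.2, 6.1 or 13.0 points for 2014-2018. Anything larger overall depends on record lengths that the documents do not give. The side comparison of occurrence is not shown to be compromised. If follow-up did differ by side it could be, but the documents give no evidence either way.

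**What to change.** Before extraction, add these dates to the list in section 6: first levothyroxine, first recorded hypothyroidism, last contact and, where recorded, death.

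In section 6.1:
- State first levothyroxine as the working definition of need, which the plan leaves undefined. Analyse time from surgery to that date by Kaplan-Meier and by a Cox model for side with the covariates already named there, censoring at last contact. Where cumulative incidence is reported, treat death before the event as a competing event.
- Leave patients already on levothyroxine at surgery out of this time-to-event analysis and report their number. Section 4.2 does not exclude them from the study.
- Report occurrence of hypothyroidism from its own date, by the same method, at one time point fixed before the data are opened.
- If time among starters is described, label it as conditional on starting and limited by follow-up.
- State non-informative follow-up as an assumption. Add one sensitivity analysis that counts patients lost before the chosen time as event-free, which gives a lower figure.

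The cost is SAP wording and a few more dates per patient from records already being read. Some dates will be missing in older records, and that number should be reported. Estimates remain biased if length of record depends on treatment: in step 6 of the working, Kaplan-Meier gave 19.5% or 14.1% against a true 16.5%.
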